9.8.4 Efficacy analysis

- Secondary objective/endpoint : achievement of target objective at 12 weeks, per component

Evaluation at week 12/16 of the level of achievement of the main treatment goal identified by the patient in the table at baseline. This evaluation will be performed using a Likert scale in 4 points (“very satisfied”, “satisfied”, “unsatisfied”, “very unsatisfied”).

The achievement of the main treatment goal will be defined as a “satisfied or very satisfied” response.

It will be described on the efficacy population.

- The proportion of patients with achievement of the main treatment goal will be described and the confidence interval at 95% will be provided.
- The primary analysis will be performed with considering missing data as non responder, and a sensitivity analysis will be performed on patients without missing data (observed case).
- Search for predictive factors of efficacy.

The predictive factors of the achievement of the main treatment goal on completed patients will be searched among baseline characteristics using binary logistic regressions models. Univariate analyses will be used to select ($p\text{-value} \leq 0.20$) the explanatory variables to include

in the multivariate model. The results of univariate and multivariate analyses will be interpreted in terms of odds-ratios with their 95% confidence intervals

In case of correlated variables, only the more significant in univariate will be include in the multivariate model.

Variables with a rate of missing data $\geq 20\%$, or those with empty categories or with very small number will not be considered eligible for this research of predictive factors.

As part of one of the secondary objectives, the analyses performed for the efficacy endpoint are summarized in the table below :

Objective	Statistical analysis	Exposure measure	Outcome measure	Covariables
2.a	Proportions	N/A	Achievement of the main goal (yes /no) at 12/16 weeks	N/A
2.b	Proportions – sensitivity analysis	N/A	Achievement of the main goal (yes /no) at 12/16 weeks	N/A
2.c	Binary logistic regression models,	N/A	Achievement of the main goal (yes /no) at 12/16 weeks	Relevant confounders (eg : demographic data, medical history, previous treatment...)
2.d	Proportions	N/A	Achievement of the main goal (yes /no) at 12/16 weeks for each component	N/A

9.8.5 Other secondary analyses

- Description and evolution of PASI

The PASI score will be described at baseline, W12/16 and W52.

The change in the PASI score between baseline and W12/16 then between baseline and W52 will be described by summary descriptive statistics, including 95% confidence interval of the mean.

- Evolution of DLQI

The change in the DLQI score between baseline and W12/16 then between baseline and W52 will be described by summary descriptive statistics, including 95% confidence interval of the mean.

- Level of agreement between the dimensions reported by the patient and by the treating physician.

The proportion of concordant / discordant choices between the dimensions selected at baseline by patient and the physician will be described.

The level of agreement could be evaluated with a Kappa coefficient. Results will be provided in both a quantitative and a qualitative way using the following classes : <0 =« no agreement », [0 ; 0.20]=[« slight agreement »,]0.20 ; 0.40]=[« fair agreement »,]0.40 ; 0.60]=[« moderate agreement »,]0.60 ; 0.80]=[« substantial agreement » et]0.80 ; 1]=[« almost perfect agreement ».

- Maintenance of target objective at W52

The Maintenance of the main treatment goal will be defined as a “satisfied or very satisfied” response at W52 for patients who have achieved their initial treatment goal at W12/16.

The proportion of patients with maintenance of their main treatment goal at W52 will be described.

- Change of therapeutic objective at the 1st follow-p visit (W12/16).

The proportion of patients who changed their main treatment goal at W12/16 will be described.

- Level of accordance between PASI \geq 90 and the satisfaction level in regard to the therapeutic objective set by the PSO-TARGET QoL Component grid.
- The change in the PASI score between baseline and the 1st follow-up visit (W 12/16) will be described according to the level of achievement of the main treatment goal (achieved or not). The percentages of patients with a PASI \geq 90 that responded “satisfied or very satisfied” on the Likert scale at 12 weeks will be calculated and will be compared to the percentages of patients with a PASI \geq 90 that responded “unsatisfied or very unsatisfied”, using a χ^2 analysis. In case the populations are too small, a Fisher exact test will be used.

The analyses performed for the secondary endpoints are summarized in the table below :

Objective	Statistical analysis	Exposure measure	Outcome measure	Covariables
1	Contingency table; Sensitivity / Specificity	N/A	Concordance level between PSO- TARGET Component grid and DLQI at 12/16 weeks	N/A

Objective	Statistical analysis	Exposure measure	Outcome measure	Covariables
2.a	Proportions	N/A	Achievement of the main goal (yes /no) at 12/16 weeks	N/A
2.b	Proportions – sensitivity analysis	N/A	Achievement of the main goal (yes /no) at 12/16 weeks	N/A
2.c	Binary logistic regression models,	N/A	Achievement of the main goal (yes /no) at 12/16 weeks	Relevant confounders (eg : demographic data, medical history, previous treatment...)
2.d	Proportions	N/A	Achievement of the main goal (yes /no) at 12/16 weeks for each component	N/A
3.a	Means	N/A	Description and evolution of PASI score at 12/16 then 52 ± 4 weeks	N/A
3.b	Mixed effect model with repeated measurement	N/A	Evolution of PASI score over the 52 ± 4 weeks	PASI score at baseline
3.c	Means	N/A	Description and evolution of DLQI score at 12/16 then 52 ± 4 weeks	N/A
3.d	Mixed effect model with repeated measurement	N/A	Evolution of DLQI score over the 52 ± 4 weeks	DLQI score at baseline
3.e	Proportions. Khi-Square analysis	N/A	PASI≥90 versus satisfaction level (QoL Component grid)	
4.a	Proportions	N/A	Proportion of concordant choices (yes /no)	N/A
4.b	Kappa coefficient	N/A	Agreement for the selected dimension between patient and physician	N/A
5.a	Proportions	N/A	Maintenance of the main goal (yes /no) at 52 ± 4 weeks	N/A

Objective	Statistical analysis	Exposure measure	Outcome measure	Covariates
6.a	Proportions	N/A	Change of the therapeutic objective (yes /no) at 12/16 weeks	N/A

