THIS DOCUMENT CONTAINS TRADE SECRETS, AND/OR COMMERCIAL OR FINANCIAL INFORMATION, PRIVILEGED OR CONFIDENTIAL, DELIVERED IN CONFIDENCE AND RELIANCE THAT SUCH INFORMATION WILL NOT BE COPIED OR MADE AVAILABLE TO ANY THIRD PARTY WITHOUT THE WRITTEN CONSENT OF LEO PHARMA A/S

baseline. The therapeutic objective achievement is defined as “satisfied” or “very satisfied” response on 4 points Likert scale.

- Level of concordance between the satisfaction level in regard to the therapeutic objective set by the PSO-TARGET QoL Component grid and the DLQI at the 2nd follow-up visit (52 ± 4 weeks.).
- Research of predictive factors (among baseline characteristics) of the achievement of the main treatment goal.
- Percentage of agreement between the physician-reported and the patient-reported dimensions at the first follow-up visit.
- Rate of patients having changed objective at the 1st follow-up visit (12/ 16 weeks).
- Percentage of patients who have maintained at 52 ± 4 weeks the level of satisfaction achieved at the 1st follow-up visit.
- PASI Scores at baseline, at the 1st follow-up visit (12/ 16 weeks), at the 2nd follow-up visit (52 ± 4 weeks.).
- Level of accordance between PASI 90/100 and the satisfaction level in regard to the therapeutic objective set by the PSO-TARGET QoL Component grid.
- DLQI Scores at baseline, at the 1st follow-up visit (12/ 16 weeks), at the 2nd follow-up visit 52 ± 4 weeks.

Data sources

Patients' data will be collected at day 0, at the 1st follow-up visit (12/16weeks) and at the 2nd follow-up visit at 52 ± 4 weeks according to the physician's practice.

As a prospective study, the following data will be collected during the patient visit: disease history, concomitant treatments, previous anti psoriatic treatment and adverse events. In addition, the following study specific data will be collected: disease severity (PASI score), quality of life questionnaires (DLQI, PSO-TARGET component grid).

Study size

The main criterion is the sensitivity of the PSO-TARGET tool (percentage of patients who consider their target objective as being achieved after 12/16 weeks of treatment as defined by a “satisfied or very satisfied” response, assessed on a 4 points Likert scale, among patients with a DLQI total score of 0 or 1).

The sample size calculation is based on the following hypotheses :

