8.2 Secondary Objectives

- Evaluate the percentage of patients who consider their target objective as being achieved after 12/16 weeks of treatment as defined by a "satisfied or very satisfied" response.
- Level of concordance between the satisfaction level in regard to the therapeutic objective set by the PSO-TARGET QoL Component grid and the DLQI at the 2nd follow-up visit (52 ± 4 weeks.).
- Evaluate the level of agreement between the dimensions reported by the patient and by the treating physician at baseline.
- Follow the degree of completeness of the main treatment goal identified at baseline after 52 weeks.
- Follow evolution of the PASI score (at 12/16 and 52 weeks).
- Level of accordance between PASI 90/100 and the satisfaction level in regard to the therapeutic objective set by the PSO-TARGET QoL Component grid.
- Follow evolution of the DLQI score (at 12/16 and 52 weeks).
- Evaluate the rate of patients who change their therapeutic objective after 12/16 weeks of treatment.

9 Research Method

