9.8.3 Sensitivity/sensibility analysis

- Analysis of the primary endpoint

The primary endpoint will be the evaluation at week 12/16 of the sensitivity and the specificity, compared to the DLQI as a standard, of the PSO-TARGET QoL component grid to assess the level of satisfaction of patient achieving the therapeutic goal, identified by himself.

The therapeutic objective will be considered as achieved if the patient gives the responses “Satisfied” or “Very Satisfied” on the Likert scale. The response will then be compared to the DLQI score at 12/16 weeks.

It will be described on the efficacy population.

A contingency table will be constructed as follows:

PSO-TARGET \ DLQI	0-1	2-5	6-10	11-20	21-30
Very satisfied	TP	FP	FP	FP	FP
Satisfied	TP	FP	FP	FP	FP
Unsatisfied	FN	TN	TN	TN	TN
Very unsatisfied	FN	TN	TN	TN	TN

This table can be summarized as :

PSO-TARGET \ DLQI	0-1	≥ 2
Very satisfied ou Satisfied	TP	FP
Unsatisfied ou Very unsatisfied	FN	TN

TP: True positive

FP: False Positive

FN: False Negative

TN: True Negative

The validity of the QoL component grid will then be assessed by calculating the following parameters:

Sensitivity: defined as the probability to have patients who have reached their therapeutic target (who have responded « satisfied » or « very satisfied » on the Likert scale, globally and in each major domains) among patients with a DLQI score between 0 and 1.

In other terms the sensitivity is defined as the **concordance** of the QoL component grid and the DLQI **for the patients with optimal quality of life**.

The sensitivity is calculated by:

$$Se = \frac{TP}{TP + FN}$$

Specificity: defined as the probability to have patients who have not reached their therapeutic target (who have responded « unsatisfied » or « very unsatisfied » on the Likert scale, globally and in each major domains) among patients with a DLQI score ≥2.

In other terms the specificity is defined as the **concordance** of the QoL component grid and the DLQI **for the patients with suboptimal quality of life**.

The specificity is calculated by:

$$Sp = \frac{TN}{FP + TN}$$

The QoL component grid will be validated if these two parameters reach the threshold of 85%.

THIS DOCUMENT CONTAINS TRADE SECRETS, AND/OR COMMERCIAL OR FINANCIAL INFORMATION, PRIVILEGED OR CONFIDENTIAL, DELIVERED IN CONFIDENCE AND RELIANCE THAT SUCH INFORMATION WILL NOT BE COPIED OR MADE AVAILABLE TO ANY THIRD PARTY WITHOUT THE WRITTEN CONSENT OF LEO PHARMA A/S

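### Section 9.8.5 and row 3.e answer the PASI 90 accordance objective with a badly worded chi-square/Fisher comparison, which tests association, and name no overall agreement measure

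*Protocol*

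**What the plan says.** Section 8.2 lists the objective as "Level of accordance between PASI 90/100 and the satisfaction level in regard to the therapeutic objective set by the PSO-TARGET QoL Component grid". The Abstract carries it both as an objective and as an endpoint.

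Section 9.8.5 restates it with PASI≥90 and plans two things under it. First, the PASI change from baseline to week 12/16 "will be described according to the level of achievement of the main treatment goal (achieved or not"). Second, a chi-square comparison of the satisfied share with the unsatisfied share, where the sentence attaches both shares to PASI≥90 patients. Its central words are: "on the Likert scale at 12 weeks will be calculated and will be compared to the percentages of patients with a PASI". The fallback is: "In case the populations are too small, a Fisher exact test will be used". In the summary table, row 3.e gives the method as "Proportions. Khi-Square analysis" and the outcome as "PASI≥90 versus satisfaction level (QoL Component grid").

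The protocol's other agreement questions are handled differently:

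- **Grid against DLQI (section 9.8.3).** "A contingency table will be constructed as follows", followed by sensitivity and specificity, each explained as a concordance rate.
- **Patient against physician (section 9.8.5, rows 4.a and 4.b).** The proportion of concordant choices, and a kappa coefficient with verbal classes.

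**The concern.** There are two separate problems.

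**Wording.** Both percentages in the sentence refer to PASI≥90 patients. Taken literally, they are the satisfied and unsatisfied shares of one group. They sum to 100%, form no two groups for the named tests, and leave out everyone below PASI 90.

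**Method against objective.** If an ordinary 2x2 comparison was meant, the chi-square or Fisher test is valid, but it asks whether PASI 90 response and satisfaction are related. The objective asks how far they agree. A small p-value can occur when most patients below PASI 90 are satisfied, and the chi-square statistic does not distinguish agreement from disagreement. Section 9.8 sets two-tailed testing at 0.05 for all comparisons, so a significant result could be reported as accordance when the planned test does not show that.

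**Working it through.** **Inputs.** From section 9.5: 134 evaluable patients, prevalence of DLQI 0-1 of 0.80, sensitivity 0.90. Assumed here, because the protocol gives no figure: specificity 0.90, and PASI 90 rates from 40% to 75%.

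**The plan's own figure.** The PASI analysis has no stated number. The 134 reproduces with an exact binomial test of 0.80 against 0.90 at an upper-tail level of 0.025: n1 = 107, reject at 94 or more, exact level 0.0233, power 0.819. Then 107/0.80 = 133.75, so 134.

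**Satisfied rate.** 0.80 × 0.90 + 0.20 × 0.10 = 0.74, and 0.74 × 134 = 99.2. I use 99 satisfied and 35 unsatisfied.

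**Illustrative table, PASI 90 rate about 75% (100 of 134)**

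| | PASI 90 | below PASI 90 | total |
|---|---|---|---|
| Satisfied | 79 | 20 | 99 |
| Unsatisfied | 21 | 14 | 35 |
| Total | 100 | 34 | 134 |

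- Uncorrected chi-square = 134 × (79×14 − 20×21)² / (99×35×100×34) = 134 × 686² / 11,781,000 = 5.35, p = 0.021 (Fisher 0.026).
- Overall agreement = (79 + 14)/134 = 69% (Wilson 95% CI 61-77%).
- Satisfied among responders = 79/100 = 79% (70-86%).
- Unsatisfied among non-responders = 14/34 = 41% (26-58%).
- Chance agreement = (99×100 + 35×34)/134² = 0.618. Kappa = (0.694 − 0.618)/(1 − 0.618) = 0.20.
- Largest kappa these margins allow: best possible agreement is (99 + 34)/134 = 0.993, giving 0.98. Unequal margins therefore do not explain the low kappa.

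The test is significant, yet most patients below PASI 90 are satisfied.

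**Other assumed PASI 90 rates, same 99 satisfied**

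| PASI 90 rate | p | Unsatisfied among non-responders | Agreement | Kappa | Max kappa |
|---|---|---|---|---|---|
| 60% | 0.018 | 20/54 = 37% | 63% | 0.19 | 0.69 |
| 50% | 0.011 | 24/67 = 36% | 60% | 0.19 | 0.52 |
| 40% | 0.004 | 28/80 = 35% | 56% | 0.19 | 0.38 |

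All four tables were picked to have p below 0.05 and kappa at or below 0.20, so they show what can happen, not what is likely. At a 70% rate no table meets both conditions: the neighbouring ones give p = 0.0504 with kappa 0.17, and p = 0.017 with kappa 0.205. At 40% the low kappa is partly due to the margins.

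**Direction.** With rows PASI 90 yes/no and columns satisfied yes/no, (80, 14 / 14, 26) gives chi-square 33.64, agreement 106/134 = 79% and kappa 0.50. Swapping the columns gives the same 33.64, with agreement 28/134 = 21% and kappa −0.36.

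**Literal reading of the first table.** 79/100 against 21/100, a gap of 58 points within one group. The 2x2 reading compares PASI 90 rates of 79/99 = 79.8% and 21/35 = 60.0%, a gap of 19.8 points. With no association at all, the literal shares would still be about 74% and 26%.

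**The case against.** The literal analysis is unlikely to be run. A 2x2 chi-square or Fisher test needs two groups, the preceding sentence groups by goal achieved or not, and row 3.e sets PASI≥90 against satisfaction level. This stands: the wording is a drafting slip. A reader might infer that the planned test is invalid, but the context does not support that.

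A reader might also infer that the plan names none of the rates needed. On the literal wording it does name one of them, satisfied among PASI 90 responders. On the 2x2 reading, the proportions and group sizes let a reader derive agreement and would show its direction, so the reversed table above would be noticed at once. This also stands. What remains missing is a named overall agreement measure.

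Proportions come first in row 3.e, section 9.8 allows 95% CIs where relevant, and section 9.7 provides for a revised SAP with additional analyses. The p-value would therefore not appear alone. This limits the harm but does not remove the mismatch, because section 9.8.5 itself fixes a method that does not quantify its objective.

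Finally, a reader might infer that a promised PASI 100 result has been dropped. The documents do not clearly promise one: the objective's 90/100 can be read as a range, and section 9.8.5 restates it as PASI≥90.

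**Conclusion.** The point holds as a minor one. The sentence in section 9.8.5 needs its comparison groups stated. On the intended 2x2 reading the test is valid, but it measures association, and no overall agreement measure is named for an objective called accordance, although the protocol supplies one form or another for its two other agreement questions.

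The size is illustrative. It rests on assumed PASI 90 rates, an assumed specificity of 0.90 and selected tables, which show only that a significant test and weak agreement can occur together. The harm is confined to how one secondary endpoint of an exploratory study is reported and interpreted. Sample size, the 85% decision rule and the primary result do not depend on it.

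**What to change.** In section 9.8.5 and row 3.e:

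1. Cross-classify PASI 90 response by satisfied/unsatisfied in all evaluable patients at week 12/16. Define response as at least a 90% reduction from baseline; section 9.4 gives PASI as a 0 to 72 score, so PASI≥90 cannot be a score.
2. Report overall agreement and the two conditional rates (satisfied among responders, unsatisfied among non-responders) with 95% CIs, in the form section 9.8.3 uses for the DLQI.
3. Kappa is optional. If given, note that unequal margins cap it (about 0.38 if 74% are satisfied and 40% reach PASI 90, both assumed).
4. If chi-square/Fisher is kept, state that it compares PASI 90 rates between satisfied and unsatisfied patients and tests association only.
5. A separate PASI 100 table is optional.

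The cost is protocol or SAP wording only. The data are already collected, and the table form already exists in the protocol.

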9.8.6 Safety analysis

Study AEs will be tabulated in the final report. AEs will be classified by system organ class (SOC), preferred terms (PT) in accordance with the current version of the Medical dictionary for Regulatory Activities (MedDRA), causality and seriousness.

Safety analyses will be performed on the Safety population.

9.9 Quality Control

LEO Pharma and/or its designee will monitor study data to ensure data quality and conformance to Good Clinical Practices (GCPs). Verification of Case Report Form (CRF) data to source documentation, assessment of study progress and assessment of Investigator compliance to study protocol and Ethics Committee/IRB requirements will be performed according to a pre-defined monitoring plan.

9.9.1 Data Collection

Data will be collected on printed CRFs by the investigators. The completed CRFs as well as the completed questionnaires will be sent to the CRO and entered by a data manager into a computer database developed specifically for this study.

Data will remain anonymous.

Access to the database will be restricted to personnel responsible for data entry and to data management and statistics personnel who are directly involved in the management or analysis of this study. Investigators will not have access to the computer database.

9.9.2 Data monitoring

The Monitoring Plan is a separate document, in which detailed monitoring arrangements such monitoring frequency, timing of monitoring visit, access to source data etc. are defined.

The level of source data verification will be set in the Monitoring Plan.

THIS DOCUMENT CONTAINS TRADE SECRETS, AND/OR COMMERCIAL OR FINANCIAL INFORMATION, PRIVILEGED OR CONFIDENTIAL, DELIVERED IN CONFIDENCE AND RELIANCE THAT SUCH INFORMATION WILL NOT BE COPIED OR MADE AVAILABLE TO ANY THIRD PARTY WITHOUT THE WRITTEN CONSENT OF LEO PHARMA A/S

The Clinical Research Associate (CRA) will always refer to the currently valid version of the Monitoring Plan. Monitoring will be performed by outsource consultant according to validated procedures as detailed in the Monitoring Plan.

9.9.3 Data validation

All data management activities will be described in the Data Management Plan.

During the study, data queries will be generated for data items that are potentially erroneous and require appropriate clarification or correction. Prior to database lock, statistical verification of the data will be undertaken in order to further assure data quality.

Over the course of the study, the investigator and the members of the investigator's team agree to be available during regular Quality Control visits by the Clinical Research Associate.

During these visits, the following points will be reviewed:

- Signed informed consent;
- quality of the data collected in the CRFs: accuracy, missing data, consistency of the data with the 'source' documents (medical files, appointment books, original copies of laboratory results, etc.).

9.10 Limitations of Research Methods

The complementary value of observational studies relies on their robustness for extrapolation to the background environment that they aim to represent. Thus, the study population shall be representative which means minimization of site selection bias and patient selection bias. In studies of patient treatments, the treatment must be representative, meaning the existence of the study should not impact prescription habits.

However in the current study we are observing Kyntheum® users, the estimates will be affected by selection bias, e.g. Confounding by indication and channelling bias. Those patients the dermatologist chooses to treat with Kyntheum® in the first time after launch, are likely to be the most severe patients who have failed on other treatments available (bias by indication) and those patients that are "channelized" to the study sites and further chosen as study subjects might differ systematically from that group of patients we are trying to describe (channelling bias). The influence of channelling bias is tried minimized by consecutive enrolment, ensuring that patients are not chosen by the investigator to participate in the study. Additionally we expect selection bias due to informed consent, confounding by missing data and attrition depending on disease severity.

THIS DOCUMENT CONTAINS TRADE SECRETS, AND/OR COMMERCIAL OR FINANCIAL INFORMATION, PRIVILEGED OR CONFIDENTIAL, DELIVERED IN CONFIDENCE AND RELIANCE THAT SUCH INFORMATION WILL NOT BE COPIED OR MADE AVAILABLE TO ANY THIRD PARTY WITHOUT THE WRITTEN CONSENT OF LEO PHARMA A/S

Acknowledging that the study is prone to many sources of bias and confounding, the design of this study has been optimized to reflect the patient journeys to the extent possible.

